10.3 Subsite SAE Reporting Requirements

NOTE: Subsite institutions are NOT permitted to report directly to the FDA or The Ohio State University Office of Responsible Research Practices. All reports must be sent to the OSU Principal Investigator and Subsite Coordinator for submission to the FDA and ORRP.

Subsites must report SAEs to their IRB of record as per their institutional and IRB policies.

Subsites must report all SAEs to the lead Principal Investigator and the OSU Subsite Coordinator within 24 hours of knowledge of the event. SAEs are to be reported on MedWatch 3500A form and submitted with the SAE Submission Form (refer to Supplemental Forms Document). All SAEs and unanticipated problems involving risk to subjects or others will be reported by the OSU Subsite Coordinator following institutional and FDA guidelines. In addition, all serious adverse events (SAEs) are reported by the OSU Subsite Coordinator to The Ohio State University Office of Responsible Research Practices, Medivation Inc. via ProductLife Ltd and to the Food and Drug Administration (FDA) if applicable and within the timeframes outlined in the below table. Subsite institutions are NOT permitted to directly report to The Ohio State University Office of Responsible Research Practices, Medivation Inc., ProductLife Ltd or FDA. All AE/SAEs will be reported to the DSMC at the quarterly DSMC review meetings; however, the investigator determines corrective action is necessary, and "ad hoc" DSMC meeting will be called.

Fatal adverse events related to treatment which are unexpected must be reported within 24 hours of the Investigators first awareness of the event to the OSU Principal Investigator, OSU Subsite Coordinator and Medivation Inc. via ProductLife Ltd. The OSU Subsite Coordinator will immediately report to The Ohio State University Office of Responsible Research Practices and the DSMC. Fatalities not related to the study drug/device must be reported within 5 days.

10.4 Serious Adverse Events

When the principal investigator has determined that a Serious Adverse Event has occurred, the principal investigator is responsible for providing all Serious Adverse Events to ProductLife LTD by fax [[name]] within 24 hrs of the site becoming aware of the event and to the IRB within respective required guidelines. If fax is not available, the form may be scanned and emailed to [contact]. This applies to initial and follow-up information.

Follow-up Reports:

- The Investigator should take all appropriate measures to ensure the safety of the patients, notably he/she should follow up the outcome of any Serious Adverse Event and complete follow-up forms as necessary. The patient must be followed up until recovery, stabilization or return to baseline. This may mean that follow-up will continue after the patient has completed the trial and that additional investigations may be necessary.
- Any reportable Serious Adverse Events brought to the attention of the Investigator at any time after cessation of the trial and considered by him/her to be reasonably associated with medication administered during the period should also be submitted to the IRB and to Medivation Inc via ProductLife Ltd.
- As with the initial submission to the IRB, the principal investigator is also responsible for providing all follow-ups of Serious Adverse Events to the IRB and to Medivation Inc, designated pharmacovigilance representative, ProductLife Ltd, using the forms provided by Medivation Inc. for this purpose.

10.5 Reporting of Adverse Event Information Following Study Completion

Collection of safety information following the end of investigational product administration is important in assisting in the identification of possible delayed toxicities or withdrawal effects. All SAEs must be collected which occur within 30 days of discontinuation of dosing or completion of the patient's participation in the study if the last scheduled visit occurs at a later time.

10.6 Pregnancy Statement and Use in Nursing Women

All women of childbearing potential MUST have a negative pregnancy test as required by the RevAssist program. If the pregnancy test is positive, the patient must not receive any investigational product and must not be enrolled in the study.

Definition of Childbearing Potential: For the purposes of this study, a female of childbearing potential is a sexually mature female who: 1) has not undergone a hysterectomy (the surgical removal of the uterus) or bilateral oophorectomy (the surgical removal of both ovaries) or 2) has not been naturally postmenopausal for at least 24 consecutive months (i.e., has had menses at any time during the preceding 24 consecutive months).

Thalidomide, an analog of lenalidomide causes fetal harm and birth defects when administered to a pregnant woman. There are, however no adequate and well-controlled studies of lenalidomide in pregnant women. In New Zealand white rabbits at 10 and 20 mg/kg/day, lenalidomide was maternally toxic (reduced body weight gain and feed consumption; at 20 mg/kg/day, weight loss and one abortion). Developmental toxicity at 10 and 20 mg/kg/day included reduced fetal body weights and increased postimplantation losses and fetal variations (morbidity/purple-discolored skin, undeveloped intermediate lung lobe, irregular nasal-frontal suture, and delayed metacarpal ossification)⁶⁰. The maternal and developmental no observed adverse effect levels (NOAELs) was 3mg/kg/day.

If the drug is used during pregnancy, or if the patient becomes pregnant while taking this drug, the patient should be apprised of the potential hazard to the fetus.

During the course of the trial, all patients of childbearing potential should be instructed to contact the treating physician immediately if they suspect they might have conceived a child. In addition, a missed or late menstrual period should be reported to the treating physician. If a female patient or

the treating physician suspects that the female patient may be pregnant prior to administration of study drugs, the study drugs must be withheld until the results of a pregnancy test are available. If pregnancy is confirmed the patient must not receive study medications and must be withdrawn from the study. Throughout the entire pregnancy, additional contact should be made with the patient, and in some cases with the healthcare provider, to identify spontaneous abortions and elective terminations, as well as any medical reasons for elective termination. In addition, the study investigator should include perinatal and neonatal outcome. Infants should be followed for a minimum of 4 weeks.

If a male patient is suspected of having fathered a child while on study drugs, the pregnant female partner must be notified and counseled regarding the risk to the fetus. In addition, the treating physician must follow the course of the pregnancy, including prenatal and neonatal outcome. Infants should be followed for a minimum of eight weeks.

Upon live-birth delivery, the minimum information that should be collected includes date of birth, length of pregnancy, sex of infant, major and minor anomalies identified at birth. Outcomes can be obtained via mailed questionnaires, maternal interviews, medical record abstraction, or a combination of these methods. All serious adverse event reports relating to the pregnancy, including spontaneous abortion, elective abortion and congenital anomalies, should be forwarded to the FDA & Medivation Inc. (See Safety reporting section).

It is not known whether lenalidomide or CT-011 is excreted in human milk. Because many drugs are excreted in human milk and because of the potential for serious adverse reactions in nursing infants from lenalidomide, a decision should be made whether to discontinue nursing or discontinue the drug, taking into account the importance of the drug to the mother.

10.7 Patient Withdrawal and Study Termination

A patient should be withdrawn from the trial treatment if, in the opinion of the investigator, it is medically necessary, or if it is the wish of the patient. If a patient does not return for a scheduled visit, every effort should be made to contact the patient. In any circumstance, every effort should be made to document patient outcome, if possible.

Patients should be removed from therapy if any of the following occurs:

- The occurrence of unacceptable toxicity indicating the need for cessation of treatment. Patients may continue with correlative studies.
- Patient has progressive disease while receiving treatment
- The physician feels it is in the best interest of the patient to stop treatment and the physician may determine whether to continue with correlative studies.
- Patient refusal to continue with therapy.
- Non-compliance by the patient with protocol requirements.
- Patient is lost to follow-up. If a patient does not return for scheduled visits, every effort should be made to re-establish contact. In any circumstance, every effort should be made to document patient outcome, if possible.
- Patient becomes pregnant.
- Termination of the study.

If a patient withdraws from protocol therapy, it should be clearly documented with additional notation of whether the patient has agreed to complete follow up as outlined in the protocol. Subsite

institutions must notify the OSU Subsite Coordinator as soon as possible if the patient withdraws from protocol therapy and must provide the documentation of the reason and whether the patient will complete follow up.

The reason and date of discontinuation are to be documented in the patient's medical record and in the CRF.

The investigator should complete all end of treatment procedures when a patient withdraws from treatment. All patients who discontinue the trial secondary to an adverse event should be followed until resolution, stabilization or return to a baseline condition.

Patients who fail to complete treatment for reasons other than adverse event or unacceptable toxicity may be replaced. All patients who receive one dose of study treatment should be included in any safety analysis.

The investigator may discontinue the trial at any time. Reasons for early trial discontinuation may include, but are not limited to, unacceptable toxicity of study treatment, a request to discontinue the trial from a regulatory authority or an IRB, or poor enrollment.

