5.7 Patient Withdrawal

A patient should be removed from the study whenever it is necessary to safeguard his/her welfare. Occurrence of a significant adverse event or laboratory abnormalities unexpected for these patients may also necessitate discontinuation from the study. Additional reasons for removing a patient from the study are:

- Patients who participate in another investigational drug trial
- Patients' non-compliance with the protocol that can negatively affect the treatment effect
- Patients who express a desire to withdraw from the study (the patient has the right to withdraw for any reason without prejudice)
- Evidence of progressive disease would require withdrawal of the patient from the study.
- Any other reasons deemed by the principal investigator and treating physician.
- Patients who must discontinue use of either CT-011 or lenalidomide

The reason for any patient withdrawal from the study should be recorded on the case report form (CRF) and the occurrence should be reported to the principal investigator by email. These patients who withdraw from the study in the phase II portion of the trial will not be replaced. When a patient is removed from the study, he/she will receive treatment according to the standard of care (SOC) in the medical center and will be followed-up according to the study schedule whenever possible.

A patient who is removed from the study by the investigator due to an adverse event (AE) or serious adverse event (SAE) will be followed until resolution of the toxicity to Grade 1 or baseline. All the tests that are required to assess the patient condition will be made as frequent as necessary until the AE or SAE has been resolved. Samples that have already been obtained will be processed.

A patient who withdraws consent before starting the study will not be followed up.

A patient who is removed from the study by the investigator since he/she did not keep the appointments will be hard to follow given the circumstances. The extreme situation of this occurrence is a patient who is defined as "lost to follow-up". Attempts to follow up on the subject will be made as long as the consent has not been withdrawn by the subject. Samples that have already been obtained will be processed.

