Previous studies of lenalidomide alone in a similarly defined relapsed/refractory MM patient population has shown an overall response rate of 25%, which also included the addition of dexamethasone after 2 cycles to non-responding stable disease patients. We will consider this regimen promising if the true overall response rate is 50% or greater when lenalidomide is combined upfront with CT-011. Therefore, we will test the null hypothesis that the true overall response rate (ORR) is at most 25% (reflecting a combination regimen ORR that would not be of interest) versus our alternative hypothesis that the true ORR in patients treated with this combination regimen is at least 50%.

Decision Rule: The largest response rate where this treatment regimen would be considered ineffective in this population is 25%, and the smallest response rate that would warrant subsequent studies with this proposed regimen in this patient population is 50%. The following Three-Outcome phase II study design is a modification of the standard one-stage phase II design and uses a maximum of 29 evaluable patients to test the null hypothesis that the true response rate is at most 25%. Since we will include the 6 patients treated at the MTD from the phase I portion of the trial, this will require accruing an additional 23 evaluable patients for this phase of the study. Based on this study design, there are three possible outcomes:

- **Not promising**: This regimen will be classified as not promising with respect to the response rate in this patient population if at most 9 patients have any response after 4 cycles of therapy out of the total 29 evaluable patients.
- **Promising**: This regimen will be classified as promising with respect to increasing the response rate in this patient population if at least 12 patients have an observed response to treatment after 4 cycles of therapy out of the total 29 evaluable patients. Subsequent larger confirmatory studies may be warranted.

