The proportion of responses (partial and complete) will be calculated out of all eligible patients who receive any treatment in that disease group who are included in the phase II assessment. Assuming the number of responses is binomially distributed, 95% binomial confidence intervals will also be calculated for the estimate of the proportion of responses. All adverse events will be summarized by the NCI CTCAE v. 4 criteria, and tabulated across all patients who received any treatment with a focus on severe (grade 3+) adverse events and toxicities (i.e. those deemed at least possibly related to study treatment). In addition, we will summarize the proportion of patients who received dexamethasone after being stable disease but without response after 2 cycles of therapy. We will descriptively summarize how many of these patients were converted to response after the addition of dexamethasone. Since the addition of dexamethasone is part of the overall treatment regimen that is dependent on treatment outcome at a certain time point, we will not make other adjustments to the study design to evaluate these patients separately outside of this descriptive summarization of whether or not they received the dexamethasone. We will evaluate other clinical outcomes such as progression-free survival and overall survival using the methods of Kaplan-Meier, although these analyses will be exploratory and primarily to help describe the cohort itself.

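### Sections 5.7 and 10.7 contradict each other on replacing treated phase II patients, and the 29 evaluable patients are not defined; the stated 4% type I error holds under 5.7 but not if 10.7 is applied.

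*Combined protocol and SAP*

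**What the plan says.** Replacement is covered in four places.

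- Section 5.7 (Patient Withdrawal) lists reasons for removal, progressive disease among them, and then states: "These patients who withdraw from the study in the phase II portion of the trial will not be replaced".
- Section 10.7 (Patient Withdrawal and Study Termination) lists unacceptable toxicity, progression, physician decision, refusal, non-compliance, loss to follow-up, pregnancy and study termination as grounds for ending therapy. It then states: "Patients who fail to complete treatment for reasons other than adverse event or unacceptable toxicity may be replaced". It names neither a phase nor a time limit.
- Section 4.3 requires replacement in phase I only, for patients who leave before finishing cycle 1 for reasons other than toxicity or DLT.
- Section 7.1 lets the principal investigator decide whether to replace a registered patient who never receives protocol therapy, and says such patients are evaluable for neither toxicity nor response.

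The denominator is described in three ways.

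- In the decision rule of Section 6.1.2, the regimen is not promising "if at most 9 patients have any response after 4 cycles of therapy out of the total 29 evaluable patients". It is promising with at least 12 responses and inconclusive with 10 or 11. The 29 are six phase I patients treated at the MTD plus 23 new evaluable patients.
- Later in Section 6.1.2: "The proportion of responses (partial and complete) will be calculated out of all eligible patients who receive any treatment", restricted to those included in the phase II assessment.
- Section 6.3 divides by the number of per protocol patients, a set that is not defined.

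The synopsis (Planned Sample size) caps phase II recruitment at 23.

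**The concern.** The two withdrawal sections give opposite instructions for the same patient: someone in phase II who has been treated and stops for a reason other than toxicity. The 10.7 sentence is not simply the phase I rule restated, because that rule ends with cycle 1 and is mandatory, whereas 10.7 has no time limit and is permissive.

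This matters because the reasons that would permit replacement are related to outcome. A patient who refuses, is non-compliant, is withdrawn by the physician or is lost before the cycle 4 assessment will often have no documented response. Read literally, the sentence also reaches patients who progress. Replacing such patients in an open-label, single-arm trial selects on the endpoint, and a permissive rule leaves the choice open after the outcome is known. The bias runs towards declaring the regimen promising. The denominators do not settle the matter, because none of them says whether a replaced treated patient remains among the 29.

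**Working it through.** **Inputs.** All are from Section 6.1.2 unless noted: n = 29 (6 + 23); null response rate 0.25; alternative 0.50; not promising at 9 or fewer; promising at 12 or more; stated type I error 4%, type II error 3%, eta 0.83, pi 0.87. The documents give no rate of early stopping without response, so the replacement figures below are assumptions.

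**Step 1: reproduce the plan's figures.** With X ~ Bin(29, p), no replacement:

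- type I error = P(X ≥ 12 | p = 0.25) = 0.0390
- eta = P(X ≤ 9 | p = 0.25) = 0.8337
- type II error = P(X ≤ 9 | p = 0.50) = 0.0307
- pi = P(X ≥ 12 | p = 0.50) = 0.8675

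All four agree with the stated values after rounding. The design is therefore correct as computed when 29 treated patients are fixed, which is what Section 5.7 implies.

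**Step 2: a fixed number k of treated non-responders, each replaced once, cut-off of 12 kept.** The replaced patients contribute no responses, so the count equals the number of responders among all 29 + k treated. Type I error is P(X ≥ 12) with X ~ Bin(29 + k, 0.25):

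| k replaced | Patients treated | Type I error |
|---|---|---|
| 0 | 29 | 3.90% |
| 1 | 30 | 5.07% |
| 2 | 31 | 6.44% |
| 3 | 32 | 8.04% |
| 4 | 33 | 9.87% |
| 5 | 34 | 11.93% |
| 6 | 35 | 14.21% |

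The result is the same whether the replaced patients are dropped from the denominator or kept in it with the cut-off unchanged, because only the count of 12 matters.

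**Step 3: a fraction r of non-responders among the new patients replaced and dropped until 23 remain.** The six phase I patients stay at 0.25. The null rate among the 23 becomes p′ = 0.25 / (1 − 0.75r), and about 23 / (1 − 0.75r) patients must be treated to fill the 23 places. The total is the sum of Bin(6, 0.25) and Bin(23, p′):

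| r | p′ | New patients treated (about) | P(≥ 12 of 29) | P(≤ 9 of 29) |
|---|---|---|---|---|
| 0 | 0.250 | 23 | 3.9% | 0.834 |
| 10% | 0.25/0.925 = 0.270 | 23/0.925 = 25 | 6.0% | 0.778 |
| 20% | 0.25/0.850 = 0.294 | 23/0.850 = 27 | 9.4% | 0.702 |
| 30% | 0.25/0.775 = 0.323 | 23/0.775 = 30 | 14.9% | 0.602 |

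The two models agree closely at similar numbers of replaced patients (about 2, 4 and 7 in the second). Every replacement scenario treats more than the 23 phase II patients allowed by the synopsis.

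**The case against.** The strongest reply is that the plan already protects phase II. Section 5.7 names phase II and is categorical; Section 10.7 is a general, permissive sentence in the safety chapter and can be read as referring to phase I, where replacement is planned. The 23-patient cap points the same way. Section 7.1 gives only one ground for being non-evaluable, never having been treated, and Section 6.1.2 takes the proportion over treated patients. Together these suggest that a treated patient stays in the denominator.

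Most of this stands, and it limits the point. A reader might infer that the rule has lost its 4% error. The documents do not support that, because no text says 10.7 overrides 5.7. A reader might also infer that the plan provides for swapping out patients who progress. That is a literal but contestable reading: treatment is planned to run until progression, so a progressing patient may be said to have reached the planned end rather than failed to complete, and the replacement sentence does not mention progression. Nor do the documents show what share of early leavers are non-responders. Patients with stable disease may continue treatment, and toxicity stops are excluded by 10.7 itself.

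The reply does not remove the conflict. No order of precedence is stated, and the cap is not conclusive because Section 6.1.2 asks for 23 evaluable patients. The proportion in Section 6.1.2 is restricted to patients included in the phase II assessment, which leaves open whether a replaced patient is included. If replaced patients are kept, the total exceeds 29 and the plan gives no cut-offs for it.

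**Conclusion.** The contradiction between Sections 5.7 and 10.7 is real, and so is the missing definition of the 29. The consequence is conditional. Under 5.7 the stated operating characteristics hold. If 10.7 were applied in phase II to treated patients without a documented response, one replacement would be enough to take type I error above 4%.

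The illustrative ranges are 5.1% to 14.2% for one to six replaced non-responders, and 6.0% to 14.9% for 10% to 30% of non-responders replaced among the 23. They rest on a true response rate of 25%, an unchanged cut-off of 12 and replacement numbers chosen for illustration. They show direction and sensitivity and do not estimate an error present in the plan. The point concerns the 23 new patients; the cycle 1 replacement rule of phase I is a separate matter.

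**What to change.** Reconcile the two sections in line with the phase II rule already in 5.7.

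- **Section 10.7:** limit the replacement sentence to phase I patients who leave before completing cycle 1, as in Section 4.3, and to registered patients who never receive protocol therapy, as in Section 7.1.
- **Section 6.1.2:** define the 29 by stating that every eligible treated patient in the phase II assessment stays in, and counts as a non-responder if treatment stops before a response is documented.
- **Section 6.3:** replace the undefined per protocol denominator with the same set.

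The cost is a few sentences of amendment and no extra patients. The observed response rate may be slightly less favourable, because early stops without response count against the regimen. The change should be made before phase II outcomes are known, since a choice of denominator made afterwards would be hard to defend.
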